### 2.10 PD and PK/PD analyses

No PD and PK/PD analyses are planned in the study.

### 2.11 Patient-reported outcomes

No patient-reported outcomes analyses are planned in the study.

#### 2.12 Biomarkers

No biomarker analyses are planned in the study.

## 2.14 Interim analysis

No interim analysis is planned for this study.

# 3 Sample size calculation

The sample size calculation is based on the co-primary endpoints of patient-level sensitivity and region-level specificity.

Overall, a total study sample size of approximately 195 participants will be enrolled in order to get at least 156 evaluable participants for the co-primary endpoints (i.e. those who have both an evaluable PET/CT scan and histopathology assessment and have not received any prohibited systemic antineoplastic therapy before the completion of PET/CT and surgery). These calculations were made using the software PASS 11 and R 3.6.1.

A large variability in sensitivity of PSMA-PET in the primary staging setting has been reported. Two recent systematic reviews of [Ga]PSMA PET /CT diagnostic accuracy focused on the PS population using pathology as SoT, sensitivity of 33–99% across studies has been reported (Corfield et al 2018), as well as pooled sensitivity and specificity ranges of 23-100% and 67-100% respectively (Petersen and Zacho 2020). Recent preliminary data on the diagnostic efficacy of F-18-rhPSMA-7.3 PET imaging in PS patients compared to histopathology (n=56) reported a 95% CI low bound patient. A meta-analysis on the diagnostic accuracy of CT and MRI in the staging of pelvic lymph nodes in patients with PCa). A study evaluating the diagnostic value of [Ga]PSMA PET versus CT and MRI for lymph node staging in 130 consecutive patients who got RP and PLN).

Taking all the above into consideration, an overall patient-level sensitivity of 50% and a region level specificity of 70% will be considered as unacceptably low. Hence, the sample size calculation will be performed based on the null and alternative hypotheses as follows.

#### Patient-level sensitivity

For patient-level sensitivity, the null hypothesis (H0: patient-level sensitivity p0 = 0.50) will be tested against the alternative hypothesis (H1: p1 > 0.50)Assuming a sensitivity of 0.63 under the alternative hypothesis, approximately 156 participants with primary tumor and/or metastatic PLN would achieve 90% statistical power to detect a change in sensitivity of 0.13 using a one-sided binomial test at a targeted one-sided significance level of 2.5%. Taking into account a 20% dropout rate, 195 participants can ensure the 90% statistical power.

The lower bound of the 95% CI for sensitivity should be greater than 0.50 to be considered a success.

#### **Region-level specificity**

For region-level specificity, the null hypothesis (H0: region-level specificity p0 = 0.70) will be tested against the alternative hypothesis (H1: p1 > 0.70). Assuming a specificity of 0.85 under the alternative hypothesis, approximately 123 participants (which includes 37 participants with PLN based on a 30% prevalence) would achieve 90% statistical power to detect a change in specificity of 0.15 using a one-sided binomial test at a targeted significance level of 2.5 %. Taking into account a 20% dropout rate, 154 participants can ensure the 90% statistical power.

Novartis	Confidential	Page 37 of 43
SAP Amendment 2		Study No. CAAA405A12302

The lower bound of the 95% CI for specificity should be greater than 0.70 for the study to be considered a success.

A total sample size of 195 participants can ensure 90% statistical power for patient-level sensitivity and 99% statistical power for region-level specificity resulting in an overall study statistical power of at least 89.1% ( $0.9 \ge 0.99$ ).

# 4 Change to protocol specified analyses

Minor updates to the estimand wording were made as compared to the protocol for clarification.

Blood mass concentration data were planned to be summarized per protocol as part of the PK analysis, however the conversion of radioactivity concentration to mass concentration will not be possible due to missing information of mass concentration of the drug product during the manufacturing process. Section 2.9 of the SAP clarifies the analyses that will be summarized.

# 5 Appendix

### 5.1 Imputation rules

#### 5.1.1 Study drug

The complete date of dose administration is required for this study. Completely or partially missing date will not be imputed and should be considered as a data issue and the statistician should contact the data manager of the study.

#### 5.1.2 AE, ConMeds and safety assessment date imputation

 Table 5-1
 Imputation of start dates (AE, CM) and assessments (LB, EG, VS)

Missing Element	Rule
day, month, and year	• No imputation will be done for completely missing dates
day, month	
 
If available year = year of study treatment start date then         
 
If stop date contains a full date and stop date is earlier than date of dose administration then set start date = 01JanYYYY
 
Else set start date = date of dose administration.
 
 
 
If available year > year of date of dose administration then 01JanYYYY
 
If available year < year of date of dose administration then 01JulYYYY
 

Missing Element	Rule
day	
 
If available month and year = month and year of date of dose administration then         
 
If stop date contains a full date and stop date is earlier than date of dose administration then set start date= 01MONYYYY.
 
Else set start date = date of dose administration.
 
 
 
If available month and year > month and year date of dose administration then 01MONYYYY
 
If available month and year < month year of date of dose
 

	administration then 15MONYYYY

Table 5-2	Imputation of end dates (AE, CM)
Missing Element	Rule (*=date of dose administration plus 15 days not > (death date, cut-off date, withdrawal of consent date))
day, month, and year	• Completely missing end dates (incl. ongoing events) will be imputed by the end date of the on-treatment period*
day, month	• If partial end date contains year only, set end date = earliest of 31DecYYYY or end date of the on-treatment period *
day	• If partial end date contains month and year, set end date = earliest of last day of the month or end date of the on-treatment period*

If imputed end date is < start date, set end date = start date.

Any AEs and ConMeds with partial/missing dates will be displayed as such in the data listings.

Any AEs and ConMeds which are continuing as per data cut-off will be shown as 'ongoing' rather than the end date provided.

#### 5.1.3 Other imputations

For the date of initial diagnosis, missing day is defaulted to the 15th of the month and missing month and day is defaulted to 01-Jan.

### 5.2 AEs coding/grading

Adverse events are coded using the Medical dictionary for regulatory activities (MedDRA) terminology.

AEs will be assessed according to the Common Terminology Criteria for Adverse Events (CTCAE) version 5.0.

Novartis	Confidential	Page 39 of 43
SAP Amendment 2		Study No. CAAA405A12302

CTCAE grading is by definition a 5-point scale generally corresponding to mild, moderate, severe, life threatening, and death. This grading system inherently places a value on the importance of an event, although there is not necessarily proportionality among grades (a grade 2 is not necessarily twice as bad as a grade 1).

### 5.3 Laboratory parameters derivations

Grade categorization of lab values will be assigned programmatically as per NCI Common Terminology Criteria for Adverse Events (CTCAE) version 5.0 (specify version used in the RAP). The calculation of CTCAE grades will be based on the observed laboratory values only, clinical assessments will not be taken into account. The criteria to assign CTCAE grades are given in Novartis internal criteria for CTCAE grading of laboratory parameters. The latest available version of the document based on the underlying CTCAE version 5.0 at the time of analysis will be used. For laboratory tests where grades are not defined by CTCAE v5.0, results will be graded by the low/normal/high (or other project-specific ranges, if more suitable) classifications based on laboratory normal ranges.

A severity grade of 0 will be assigned for all non-missing lab values not graded as 1 or higher. Grade 5 will not be used. For laboratory tests that are graded for both low and high values, summaries will be done separately and labelled by direction, e.g., sodium will be summarized as hyponatremia and hypernatremia.

#### Imputation Rules

CTC grading for blood differentials is based on absolute values. However, this data may not be reported as absolute counts but rather as percentage of WBC.

If laboratory values are provided as '<X' (i.e. below limit of detection) or '>X', prior to conversion of laboratory values to SI unit, these numeric values are set to X.

The following rules will be applied to derive the WBC differential counts when only percentages are available for a xxx differential

xxx count = (WBC count) \* (xxx %value / 100)

Further derivation of laboratory parameters might be required for CTCAE grading. For instance, corrected calcium can be derived using the reported total calcium value and albumin at the same assessment using the following formula:

Corrected Calcium (mmol/L) = Calcium (mmol/L) + 0.02 [40 (g/L) - Albumin (g/L)]

For calculation of laboratory CTC grades 0 and 1, the normal range for derived corrected calcium is set to the same limits (in mg/dL) as for calcium.

CTC grades for the derived absolute WBC differential counts (neutrophils, lymphocytes) and corrected calcium will be assigned as described above for grading

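### SAP 5.3 derives corrected calcium in mmol/L but sets its normal limits for CTC grades 0 and 1 in mg/dL, with no conversion step (minor)

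*SAP*

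**What the plan says.** The relevant text is in SAP section 5.3, under Imputation Rules. The derivation is offered as an example of what grading may need: "corrected calcium can be derived using the reported total calcium value and albumin at the same assessment". The formula, quoted up to its closing brackets, is "Corrected Calcium (mmol/L) = Calcium (mmol/L) + 0.02 [40 (g/L) - Albumin (g/L". The result is therefore in mmol/L.

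The next sentence begins "For calculation of laboratory CTC grades 0 and 1" and continues "the normal range for derived corrected calcium is set to the same limits (in mg/dL) as for calcium". The section then closes by saying that corrected calcium receives CTC grades under the rules just described.

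Three other statements bear on this:

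- Grading is done by program: "Grade categorization of lab values will be assigned programmatically as per NCI Common Terminology Criteria for Adverse Events (CTCAE) version 5.0". SAP 2.8.3 adds that it uses observed values only, without clinical assessment.
- The thresholds are held elsewhere: "The criteria to assign CTCAE grades are given in Novartis internal criteria for CTCAE grading of laboratory parameters".
- SI conversion is mentioned once, in the rule for values reported as below or above a limit: "prior to conversion of laboratory values to SI unit, these numeric values are set to X". That refers to laboratory values and says nothing about normal limits.

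Calcium and albumin are both in the chemistry panel (protocol Table 8-4), so the inputs to the formula are collected.

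**The concern.** A value on one scale is to be judged against limits on another, and the two scales differ about fourfold. The sentence is an operative rule: it assigns the limits that separate grade 0 from grade 1, and a program applies them. For tests with CTCAE grades, SAP 2.8.3 builds both the worst post-baseline grade summary and the baseline-to-worst shift table on the assigned grades. SAP 5.3 also says "For laboratory tests that are graded for both low and high values, summaries will be done separately and labelled by direction", so an error in direction would appear in two sets of tables. At stake is the calcium part of the laboratory safety summaries, which support the secondary objective of safety and tolerability.

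**Working it through.** The plan states no figure on this point, so there is nothing to reproduce. The check is a unit check.

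**From the documents.** Corrected calcium = Ca + 0.02 × (40 − albumin), with Ca in mmol/L and albumin in g/L. The limits are the calcium limits in mg/dL; no numbers are given.

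**Assumed, not in the documents.** 1 mmol/L of calcium = 4.008 mg/dL. Normal ranges of 8.0-10.0, 8.5-10.5 and 9.0-11.0 mg/dL. Twelve total calcium values from 1.5 to 4.0 mmol/L, each with albumin of 20, 40 and 50 g/L, which makes 36 combinations. The grid spans the scale; it is not a forecast of the data.

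**Step 1: range of the derived value.** The smallest is 1.5 + 0.02 × (40 − 50) = 1.3 mmol/L. The largest is 4.0 + 0.02 × (40 − 20) = 4.4 mmol/L.

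**Step 2: literal comparison.** The largest value, 4.4, is below the smallest assumed lower limit, 8.0. So all 36 combinations are low under each of the three ranges, and none exceeds an upper limit.

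**Step 3: one unit.** Under 8.5-10.5 mg/dL the limits become 8.5 / 4.008 = 2.12 and 10.5 / 4.008 = 2.62 mmol/L. Examples:

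| Ca (mmol/L) | Albumin (g/L) | Corrected (mmol/L) | Literal | Corrected × 4.008 (mg/dL) | One unit |
|---|---|---|---|---|---|
| 1.75 | 40 | 1.75 | low | 7.01 | low |
| 2.40 | 40 | 2.40 | low | 9.62 | normal |
| 2.20 | 20 | 2.60 | low | 10.42 | normal |
| 2.80 | 40 | 2.80 | low | 11.22 | high |
| 4.00 | 20 | 4.40 | low | 17.64 | high |

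Over the whole grid this range gives 10 low, 10 normal and 16 high, against 36 low on the literal reading. Low, normal and high all occur under the other two ranges as well.

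**Step 4: how far from the boundary.** To reach a lower limit L literally, total calcium must be L − 0.02 × (40 − albumin). For L = 8.0 and albumin 20 g/L that is 8.0 − 0.4 = 7.6 mmol/L. For L = 9.0 and albumin 40 g/L it is 9.0 mmol/L. Both are well above the largest calcium tried, 4.0 mmol/L, so the result does not depend on which of the three ranges is used.

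**Step 5: which part is at odds.** The formula carries mmol/L and g/L throughout and is consistent in its own units. Only the unit attached to the limits conflicts with it.

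**The case against.** The best reply is that this is a leftover unit label. Reusing the calcium limits tells the programmer to borrow the calcium reference range, because a derived analyte has none of its own. The section already assumes conversion of values to SI units. A table with every participant low at baseline would be noticed in any output review, and the SAP's document history places this version after a dry run. The documents do not say that calcium tables were checked then, but the reply is plausible. It makes misgrading a risk of the literal reading and not an established result. It does not make the sentence correct, and the SAP should not depend on a programmer overriding it.

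A reader might go further and infer that every participant will be graded hypocalcaemic at every visit, that a real fall would be hidden, and that hypercalcaemia could never be seen. The documents do not support this, for three reasons:

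- The sentence covers grades 0 and 1 only. Criteria for higher grades are in the sponsor document, and nothing shows that they use the mg/dL limits. A marked rise or fall could still receive a higher grade.
- The derivation is optional in its wording and is given as an example. That calcium and albumin are measured does not show that corrected calcium is derived for every sample.
- Measured calcium keeps its own range. SAP 2.8.3 lists all laboratory data with abnormalities flagged. Protocol 8.4.1 and 10.1.1 have investigators review laboratory reports and record clinically significant abnormalities as adverse events, whatever the programmed grade.

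These points limit the harm. They do not repair the worst-grade and shift tables for corrected calcium where it is derived, because those are built from the programmed grades.

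**Conclusion.** The unit mismatch is real and can be seen in the text without any outside source. Applied literally, the rule leaves no plausible corrected calcium at grade 0, and a grade 1 high defined by the upper limit could not be assigned. The tables for corrected calcium would then be wrong at the grade 0/1 boundary wherever the derivation is used. The numerical part rests on an assumed conversion factor and three assumed normal ranges, and it is the same under all three. How grades above 1 would be affected cannot be determined from the SAP.

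Severity is minor: one analyte, in secondary safety tables, with measured calcium still visible elsewhere. The co-primary endpoints, the sample size and the success rule are untouched.

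**What to change.** Change the unit in the SAP 5.3 sentence so that value and limits agree before grading. For example: *for grades 0 and 1, corrected calcium is compared with the laboratory's calcium limits expressed in mmol/L*. Alternatively, keep the limits in mg/dL and add a step that converts the derived value to mg/dL. Also confirm which unit the grading program uses and that the sponsor's grading criteria are applied in that unit. If programming is already complete and uses a common unit, only the SAP text needs correcting. The cost is one phrase and one program check; no new data are needed and participants are not affected.

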# 5.4 Statistical models

### 5.4.1 Analysis supporting primary objective(s)

Patient-level sensitivity and two-sided exact binomial 95% CIs will be calculated.

Novartis	Confidential	Page 40 of 43
SAP Amendment 2		Study No. CAAA405A12302

Only pelvic lymph node regions will be used to calculate the specificity. Region-level specificity and two-sided exact binomial 95% CIs will be calculated.

Exact binomial confidence intervals (implemented using SAS procedure FREQ with EXACT statement for one-way tables) will be calculated (Clopper and Pearson 1934).

The supplementary analyses for the co-primary endpoints of patient-level sensitivity and region-level specificity and the corresponding 95% CIs will be calculated based on a covariateadjusted logistic regression model. The LOGISTIC procedure in SAS will be used to implement the logistic regression model adjusting for covariates. This analysis will be applied to each of the three central reader via the (BY READER) statement.

The predicted probability and 100  $(1-\alpha)$ % confidence limits for patient-level sensitivity  $P_{Sens}$  for each central reader can be obtained from SAS using the logistic regression model with covariates.

$$Logit (P_{Sens}) = \log \left\{ \frac{P_{Sens}}{1 - P_{Sens}} \right\} = \alpha + \beta_1 X_{PSA} + \beta_2 X_{Gleason \, Grp \, 2} + \beta_3 X_{Gleason \, Grp \, 3} + \beta_4 X_{Gleason \, Grp \, 4} + \beta_5 X_{Gleason \, Grp \, 5} + \beta_6 X_{PLNs}$$

The predicted probability and 100  $(1-\alpha)$ % confidence limits for region-level specificity  $P_{Spec}$  for each central reader can be obtained from SAS using the logistic regression model with covariates.

 $Logit (P_{Spec}) = \log \left\{ \frac{P_{Spec}}{1 - P_{Spec}} \right\} = \alpha + \beta_1 X_{PSA} + \beta_2 X_{Gleason \, Grp \, 2} + \beta_3 X_{Gleason \, Grp \, 3} + \beta_4 X_{Gleason \, Grp \, 4} + \beta_5 X_{Gleason \, Grp \, 5} + \beta_6 X_{PLNs}$ 

#### 5.4.2 Analysis supporting secondary objective(s)

For patient-level efficacy endpoints, their estimation and two-sided exact binomial 95% CIs will be calculated (implemented using SAS procedure FREQ with EXACT statement for one-way tables) (Clopper and Pearson 1934).

Only pelvic lymph node regions will be used to calculate region-level efficacy endpoints, and their estimation and two-sided exact binomial 95% CIs will also be calculated.

For inter- and intra-reader variability, 95% CIs will be calculated based on normal approximation with details given in Section 2.6.2.

